 Health plan beneficiary numbers	 Survey / Questionnaire responses
 Account numbers	 Billing records
 Certificate and/or license numbers	 HIV testing or infection records
 Vehicle identifiers and serial numbers, including license plate numbers	 Sickle cell anemia information
 Device identifiers and serial numbers	 Alcoholism or alcohol use information
 Web Universal Resource Locators (URLs)	 Drug abuse information
 Internet Protocol (IP) address numbers	 Mental health (not psychotherapy) notes
 Biometric identifiers, including finger & voice prints	 Psychological test results
 Full-face photographic images and any comparable images	 Genetic testing
 Any other unique identifying number, linked study ID, characteristic, or code, describe: study ID number	 Other, describe:

2. Data and/or Specimen Acquisition:

Data for this study will be collected through (*check all that apply*):

Prospective data and/or specimen collection obtained from participants. Aim 1 patient data will be obtained through a 60-minute, semi-structured interview. Aim 1 VA staff data will be obtained through a 30-minute, structured interview. No data collection is involved in Aim 2.

Retrospective data collection and/or specimens obtained from medical chart review/data access. Describe how data will be obtained (e.g., fileman, CDW, etc.):

Aim 1: In accordance with a Waiver or Alteration of HIPAA Authorization, names, addresses, telephone numbers, social security numbers, and diagnostic information of potential participants will be obtained from the VA’s Regional Data Warehouse. For study Aim 2, health data will be obtained from VA’s Corporate Data Warehouse.

Retrospective data collection and/or specimens obtained from an IRB-approved data and/or specimen repository. Indicate the repository source including name, VA location, and IRB number: Aim 1b: Survey data from Duke University Health System will be shared with the VA team via a VA-owned thumbdrive.

Note: for data and/or specimens obtained from a VA approved data repository, a Data Use Agreement (DUA) must be executed prior to obtaining data and/or specimens. See VHA Handbook 1200.12 for further information.

3. Level of Data:

The following level(s) of data will be acquired/maintained for this study (*check all that apply*):

- Identified (e.g., names, addresses or other identifiers included)
- Coded (direct and/or all identifiers removed, but study code/ID included)
- De-Identified (all HIPAA 18 and study ID/code removed):
 - Verified Statistically
 - OR
 - Verified by Absence or Removal of HIPAA 18 and study ID

- Limited Data Set
 Other: Describe:

4. Location of Data and/or Specimens, and Data Retention Plan:

A. Data and/or Specimen Location:

Aims 1 & 3:

Data will be stored electronically in \\vhadurhsmcifs01.v06.med.va.gov\Mesh. For Aim 1, data that will be stored electronically include name, address, phone number, social security number, amount of study payment earned, and date of visits (in Study Logbooks location). The study logbook will contain the key connecting PHI and the study identification number. Paper records of data include study consent form and HIPAA authorization (identified) and interview notes (coded); these will be stored in a locked filing cabinet in a locked office suite in Bldg. 1, Room C10006 or Building 8, Room 206 of the main Durham VA Health Care System campus. Audio recordings of qualitative interviews and to establish interrater reliability will be captured using an Olympus DM-620, which is a newer model of the Olympus DM-420 (see RBD 34), or will be captured using the Audacity program. When not in use, the audio recorder will be stored in a locked file cabinet in our study offices in Bldg. 1, C10006. Recordings will be moved from the audio recorder to the "Study Logbooks" location listed above; our laboratory has sanctuary exemption to allow these devices to plug into the network, as they are used in other current research projects. Audio recordings using Audacity will be immediately stored in the "Study Logbooks" location listed above. For long term storage, audio recordings may be moved to an encrypted DVD that is password-protected. Any encrypted DVDs will be stored in a locked filing cabinet in a locked office. Transcriptions from the study interviews will be stored electronically at the Study Logbooks location listed above. Data received from Duke University Health System will be moved to <\\vhadurhsmcifs01.v06.med.va.gov\Mesh> for storage and analysis.

Aim 2:

Data collected via a DART pull will be stored locally at <\\v06.med.va.gov\DUR\Mesh>.

Data will be also be placed at the VA Informatics and Computing Interface (VINCI; <http://vaww.vinci.med.va.gov/vincicentral/VINCIWorkspace.aspx>). The VA Informatics and Computing Infrastructure is a partnership between the VA Office of Information Technology and the Veterans' Health Administration Office of Research and Development. Researchers and operations staff can use VINCI to access data and statistical analysis tools in a virtual working environment through a certified VHA network computer using the VA Intranet or Virtual Private Network (VPN).

B. Data Retention Plan

Research records will be maintained and destroyed according to the National Archives and Records Administration, Records Schedule Number: DAA-0015-2015-0004. Records destruction, when authorized, will be accomplished using the then current requirements for the secure disposal of paper and electronic records. Currently, destruction of research records (see DAA-0015-2015-0004, section 7.6 "Research Investigator Files" for materials included in research records) is scheduled for 6 years after the cut-off (the cut-off is the completion of the research project) and may be retained longer if required by other federal agencies. Records will not be destroyed without pre-notification to the facility records manager.

Other data retention plan, describe:

5. Data Access and Data Recipients:

Aims 1 & 3:

Only members of our DVAMC research team will have access to identifiers and coded data. All VA research personnel who have access to VHA records are instructed, in accordance with VA policy, on the requirements of Federal privacy and information laws and regulations, VA regulations and policies, and VHA policy. All study personnel who are VA employees working within the VA system have fulfilled all required HIPAA and other VA security and privacy policy training requirements and have agreed to follow guidelines pertaining to the protection of patient data. All research staff sign VA Rules of Behavior, and all study staff are up-to-date with VHA Privacy Policy Training and the VA Office of Cyber and Information Security Awareness Training Course. The data security and privacy procedures summarized in that course include logging off or locking the computer when walking away from it; no sharing of access codes, verify codes or passwords; not allowing anyone else to use the computer under one's password; and disposing of sensitive information using VA-approved methods (e.g., shredder bins). Access to study data will be removed for all study personnel when they are no longer part of the research team.

Aim 2:

Only [name] (PI) and study statistician will have access to identifiers and coded data. All VA research personnel who have access to VHA records are instructed, in accordance with VA policy, on the requirements of Federal privacy and information laws and regulations, VA regulations and policies, and VHA policy. All study personnel who are VA employees working within the VA system have fulfilled all required HIPAA and other VA security and privacy policy training requirements and have agreed to follow guidelines pertaining to the protection of patient data. All research staff sign VA Rules of Behavior, and all study staff are up-to-date with VHA Privacy Policy Training and the VA Office of Cyber and Information Security Awareness Training Course. The data security and privacy procedures summarized in that course include logging off or locking the computer when walking away from it; no sharing of access codes, verify codes or passwords; not allowing anyone else to use the computer under one's password; and disposing of sensitive information using VA-approved methods (e.g., shredder bins). Access to study data will be removed for all study personnel when they are no longer part of the research team.

6. Data and/or Specimen Transportation and/or Transmission for all data and/or specimens involved in the study:

- I. Data and/or specimens will not be transported or transmitted outside of Durham VAMC environment. Please note: Data will not be transported outside the Durham VA environment. Specimens will, see item IIIb below.
- II. Data and/or specimens will be transported BETWEEN sites that are under the auspices of the Durham VA Medical Center. Please describe what is being transported, who will be responsible for transporting (study titles rather than names) how it will be secured during transport, and whether additional stops will be made while transporting the data/specimens. Study mail and correspondence will be moved from HSR&D space at Legacy Tower to DVAMC, Building 1, C10006. The study coordinator will be responsible for moving these documents. Data will be secured in a briefcase or lock bag with the notice below attached. No stops will be made while transporting the documents.
 - a. Local DVAMC memorandum "Authorization to Use, Process, Store, or Transmit VA Sensitive Information Outside VA Owned or Managed Facilities" has been pre-filled out for each study team member who may transport the data and/or specimens off-site. This (these) forms are included with the IRB materials.

- b. Containers (e.g., briefcase, bin) are labeled with the following notice (label placed on the outside of container):

NOTICE!!!

Access to these records is limited to: AUTHORIZED PERSONS ONLY.

Information may not be disclosed from this file unless permitted by all applicable legal authorities, which may include the Privacy Act; 38 U.S.C. §§ 5701, 5705, 7332; the Health Insurance Portability and Accountability Act; and regulations implementing those provisions, at 38 C.F.R. §§ 1.460 – 1.599 and 45 C.F.R. Parts 160 and 164. Anyone who discloses information in violation of the above provisions may subject to civil and criminal penalties.

- III. Data and/or specimens will be transmitted to other VA sites using the following method(s):

A. Data

- Data are de-identified and thus will be sent via unencrypted e-mail or unencrypted disk (encryption is optional).
 Data are coded or contain identifiers and thus will be sent
 Other, describe:

B. Specimens

- Specimens are de-identified and thus will be sent via standard carrier (tracking is optional).
 Specimens are coded or contain identifiers and thus will be sent via VA-authorized carrier with tracking.
 Other, describe:

- IV. Data and/or specimens will be transported to non-VA/VHA sites (e.g., academic affiliates, laboratories, etc.) using the following method(s):

A. Data

- Data are de-identified and thus will be sent via unencrypted e-mail or unencrypted CD.
 Data are coded or contain identifiers and thus will be sent via <chose method of transfer such as FIPS 140-2 encrypted CD or FIPS 140-2 encrypted hard drive/flash drive> using VA—approved carrier with tracking.
 Data are coded or identified and will be uploaded to sponsor website using electronic case report form (eCRF) <insert information including sponsor name and URL and the encryption the site uses.>
 Other, describe:

B. Specimens

- Specimens are de-identified and thus will be sent via standard carrier (tracking is optional) or will be hand-delivered by research study personnel. Specify method of delivery:

 Specimens are coded and thus will be sent via VA-approved carrier with tracking or will be hand-delivered by research study personnel. Specify method of delivery:

In accordance with the HIPAA and the Privacy Act, for any coded or identifiable data or specimens released from the Durham VAMC (with the exception of Limited Data Sets), an Accounting of Disclosure (AOD) will be maintained (e.g., in a database or spreadsheet) that includes the participant's name, date of the disclosure, description of the nature of the Individually Identifiable Information (III) disclosed, purpose of each disclosure, and the name and address of the person/agency to whom the disclosure was made.

7. Risk Mitigation Strategies:

- Data are fully de-identified (stripped of HIPAA 18 and study ID/code) before being shared outside of Durham VAMC.
- Specimens are fully de-identified (stripped of HIPAA 18 and study ID/code before being shared outside of Durham VAMC.
- Direct identifiers will be maintained separately from data and or specimens by using a code to “identify” subjects. In a separate database (i.e., a “linking” or “cross-walk” database) this code will be linked to identifying subject information.
- Other, specify:

8. Suspected Loss of VA Information:

Should any incident such as theft or loss of data, unauthorized access of sensitive data or non-compliance with security controls occur it will be immediately reported according to VA policy. All incidents regarding information security/privacy incidents will be reported to the ISO and PO within 1 hour of acknowledgement of issue and done so using the VHADUR Research Events Report e-mail group ([contact]).

9. Reporting of Results:

- Reporting of results, such as in scientific papers and presentations, will never identify individual subjects. Data will be presented in aggregate and individual-level data will not be published.
- Other results reporting plan, describe:

10. Future Use of Data:

- Data will be retained for future use. This is described elsewhere in the protocol and is noted in the HIPAA authorization.
 - Future Use of data is optional (i.e., not required by the research subject).
 - Future Use of data is required for participation in the study.
- No future use of data is currently planned.

11. Use of Mail Merge Technology

- Mail merge programs will be used to generate letters and/or address labels for mailings to potential or already enrolled research subjects. The study team is aware that to reduce risk of mail merge related privacy incidents, use of mail merge programs requires a 25% accuracy check to verify that (potential) research subject name and mailing address are properly “matched”. If discrepancies are found, a 100% accuracy check is required before letters may be mailed.

DATA ANALYSES

Aim 1:

Sequential Exploratory Mixed Analysis. Qualitative data collection will constitute the initial idea-generation step in treatment development, and thus findings will be used to do the following: 1) conceptualize ways to adapt intervention content to increase its specificity and appropriateness for a population of Veteran smokers living with HIV; 2) identify additional CBT content needed to increase relevance to the population; and 3) generate relapse-prevention message content specifically needed for this population. After qualitative data collection and analysis are completed, appropriate updates will be made to the CBT treatment manual and relapse-prevention message library.

Qualitative Analysis. Data will be analyzed in two phases – an initial phase of conventional content analysis followed by an inductive, thematic approach to identify patterns in the data. Coded data will be analyzed for emergent patterns and themes that may adhere to or contradict the investigators’

expectations. Data management and coding will use NVivo8 software on VA VINCI website, or ATLAS.ti on a VA secured computer.

Quantitative Analysis. Regarding quantitative data received from Duke, data from veterans who smoke, people living with HIV who smoke, and members of the general public who smoke will be analyzed separately. First, data will be cleaned. Participants will be excluded from analysis if they meet any of the following criteria: greater than 2 endorsed bogus items, self-reported “very little” or “no” effort or attention, or a “no” response to the question “In your honest opinion, should we use your data in our analyses in this study?” After data cleaning, the following descriptive statistics will be calculated for satisfaction ratings on each SmokefreeVET message: range, mean, and standard deviation. Items falling below an 8 on mean satisfaction will be reviewed by the study staff in the context of qualitative findings to make final decisions regarding their inclusion in the final relapse-prevention message library.

Aim 2:

In order to examine disparities in healthcare delivery of smoking cessation prescriptions, we will use a longitudinal retrospective design. Generalized linear mixed modeling (GLMM) with a logit link and binomial variance will be used to determine differences by age, race, ethnicity, HIV, Hepatitis C, psychiatric disorder, and severe average pain in likelihood of pharmacotherapy dispensation during a given year. GLMMs appropriately accommodate multi-level data structures with unbalanced design for analyzing repeated observations across multiple individuals nested within clinics. Clinic- and person-level random effects will be included in statistical models to account for correlation among patients within the same clinic and repeated measurements on the same individual over time, respectively. Covariates will be assessed for collinearity before entering them simultaneously into the GLMM.

Aim 3:

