Study Protocol, Including Statistical Analysis Plan

Study Title: Mobile Evidence-Based Smoking Cessation for Veterans Living With HIV (MESH)

NCT Number: NCT04135937

Document Date: 12/18/2020

Research Protocol: Smoking Cessation Treatment Preferences among Veteran Smokers Living with HIV

Principal Investigator: [name]. (Clinician; Clinical Psychologist)

PURPOSE

The overall goal of this study is to understand and improve tobacco abstinence rates among Veteran smokers living with HIV. The specific aims of the study are to:

AIM 1a: To qualitatively explore smoking cessation treatment preferences among Veteran smokers living with HIV, and to quantitatively evaluate perspectives on relapse-prevention messages among Veterans and smokers living with HIV.

AIM 1b: To quantitatively evaluate satisfaction with relapse-prevention messages among a de-identified online sample of Veterans and smokers living with HIV, and general-population smokers.

AIM 1c: To qualitatively explore smoking cessation treatment perspectives among ID health care staff who serve Veterans living with HIV.

AIM 2: To quantitatively examine trends and determine health disparities by HIV status and demographic characteristics in use of smoking cessation aids among patients receiving VHA clinical care.

AIM 3: To use a successive cohort design to develop a mobile health (mHealth) smoking cessation intervention tailored for Veterans living with HIV.

BACKGROUND AND SIGNIFICANCE

Among the over 1 million people living with HIV in the U.S., the smoking rate is two to three times higher than in the general U.S. population (Kariuki et al., 2016; Moscou-Jackson, Commodore-Mensah, Farley, & DiGiacomo, 2014). Population-based estimates indicate that roughly 2 of every 5 U.S. adults with HIV endorse current cigarette smoking, which far exceeds the 20% smoking prevalence rate in the general population (Mdodo et al., 2015). Furthermore, despite generally declining smoking rates in the U.S., rates of smoking among people living with HIV have remained virtually unchanged over the past 20 years (Cooperman, 2016). This is likely due to the fact that compared to the general adult population, individuals with HIV are less likely to quit (Mdodo et al., 2015).

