For this study aim, the data source will be a data request from Corporate Data Warehouse (CDW). Health data, which may include PHI (e.g., dates of care), will be gathered from 2014 to present. After requesting data access via the Data Access Request Tracker (DART), Veterans with and without HIV (per ICD-9 and ICD-10 diagnosis codes) will be identified from VA's Regional and/or Corporate Data Warehouse. During the retrospective observation period, tobacco use will be determined annually (January 1 through December 31 for each year) for each patient based on a validated algorithm for identifying smoking status from the EMR (Calhoun et al., 2017; McGinnis et al., 2011). Data will be extracted on tobacco use health factors, pharmacy records of medications dispensed, primary care/ID clinic outpatient healthcare encounters, pain intensity vital sign data, patient demographics, and diagnosis codes for comorbid disorders of interest (Hepatitis C coinfection and psychiatric disorders). For each year in which patients are determined to be smoking, three outcomes will be assessed: pharmacy dispensation of NRT, bupropion, or any smoking cessation pharmacotherapy (NRT, bupropion, or varenicline). Specifically, pharmacotherapy dispensation will be coded dichotomously (yes/no) based on presence/absence of a pharmacy record within each 12-month observation period.

We will examine a range of variables to detect disparities in pharmacotherapy utilization. Demographic information will include age, race, and ethnicity. HIV, Hepatitis C, and psychiatric disorder will be based upon the ICD-9 and ICD-10 codes. Given previous work in the area of treatment access disparities, we will include the following psychiatric disorders as variables: psychotic disorder, bipolar disorder, PTSD,

other anxiety/mood disorder, and any substance use disorder (all time-invariant, coded in year 1). Pain is coded 0-10 at each VHA healthcare visit as the fifth vital sign, and will be averaged over each 12-month monitoring period and dichotomized as severe (≥ 7) vs. mild/moderate (0-6) (Volkman et al., 2015). Number of clinic visits attended each year will be collected to control for the likelihood that more clinic visits convey a higher probability of pharmacotherapy.

AIM 3 METHODS

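### The Aim 2 variable list and mixed model do not name sex, so the specified analysis gives no sex contrast and an HIV odds ratio not adjusted for sex

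*Combined protocol and SAP*

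**What the plan says.** The Purpose section sets Aim 2 to "determine health disparities by HIV status and demographic characteristics in use of smoking cessation aids among patients receiving VHA clinical care". The closing paragraph of Background and Significance repeats this.

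Aim 2 Methods describes a data request that covers, among other items, "pain intensity vital sign data, patient demographics, and diagnosis codes for comorbid disorders of interest". It then lists the variables to be examined for disparities. On demographics it says "Demographic information will include age, race, and ethnicity". HIV, Hepatitis C, a set of psychiatric disorders and severe pain follow. One further variable is there for adjustment only: "Number of clinic visits attended each year will be collected to control for the likelihood".

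The Aim 2 paragraph of Data Analyses specifies a generalized linear mixed model with a logit link and random effects for clinic and person, to determine "differences by age, race, ethnicity, HIV, Hepatitis C, psychiatric disorder, and severe average pain in likelihood of pharmacotherapy dispensation" in a given year. On model building it adds "Covariates will be assessed for collinearity before entering them simultaneously into the GLMM".

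**The concern.** The aim is worded for demographic characteristics in general, but both places that turn it into variables stop at the same three. Sex is a basic demographic variable, and no reason is given for leaving it out. The plan states its contrasts one by one, so an analyst who follows it would not report sex. A sex result added later would be unplanned.

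There is also an adjustment question. Covariates enter together, so the HIV odds ratio is adjusted only for what is entered. If the sex mix differs between Veterans with and without HIV, and dispensing differs by sex, part of the apparent HIV difference would be a sex difference.

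**Working it through.** **Text check.** Aim 2 states no sample size, power, significance level or expected effect, so there is no figure to reproduce. The check is a comparison of the places that define the analysis.

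| Place | Demographic content | Sex or gender named? |
|---|---|---|
| Purpose, Aim 2 | demographic characteristics, in general | no |
| Aim 2 Methods, extraction | patient demographics, not itemised | no |
| Aim 2 Methods, variables examined | age, race, ethnicity | no |
| Data Analyses, Aim 2 model | age, race, ethnicity | no |

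Aim 2 Methods identifies Veterans with and without HIV by diagnosis codes. It describes no matching and no restriction by sex, so nothing in the design replaces the missing covariate.

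**Size of the possible shift in the HIV odds ratio.** All inputs are assumptions, because the documents give none of them:

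- share of women among HIV-positive smokers, w1 = 0.03;
- share of women among HIV-negative smokers, w0 = 0.08 or 0.15;
- female-to-male odds ratio for dispensing, OR = 0.67 or 1.5.

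Approximate factor by which the HIV odds ratio is multiplied when sex is omitted:

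factor = (w1 × OR + 1 − w1) / (w0 × OR + 1 − w0)

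- OR = 1.5, w0 = 0.08: 1.015 / 1.040 = 0.976
- OR = 1.5, w0 = 0.15: 1.015 / 1.075 = 0.944
- OR = 0.67, w0 = 0.08: 0.9901 / 0.9736 = 1.017
- OR = 0.67, w0 = 0.15: 0.9901 / 0.9505 = 1.042

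The range is 0.944 to 1.042.

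**Check on the approximation.** The formula treats the odds ratio as a risk ratio. An exact version needs one more assumption, the dispensing rate in men. Take 20%, a true HIV odds ratio of 1.00, women 3% versus 15%, and a sex odds ratio of 1.5:

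- odds in men 0.20 / 0.80 = 0.25; odds in women 0.25 × 1.5 = 0.375; risk in women 0.375 / 1.375 = 0.2727
- risk with HIV: 0.03 × 0.2727 + 0.97 × 0.20 = 0.2022
- risk without HIV: 0.15 × 0.2727 + 0.85 × 0.20 = 0.2109
- apparent HIV odds ratio: (0.2022 / 0.7978) / (0.2109 / 0.7891) = 0.948

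This agrees with the approximate 0.944.

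**Wider assumptions.** The exact version was also run for female shares (HIV / no HIV) of 3%/6%, 3%/10%, 3%/15% and 5%/20%, sex odds ratios from 0.67 to 2.0, and dispensing rates in men of 10% to 30%. A true HIV odds ratio of 1.00 then appears as 0.88 to 1.06. The low end needs women at 5% versus 20%, a sex odds ratio of 2.0 and a rate of 10% in men. These are two-group calculations without the other covariates or the random effects, so they show order of magnitude only.

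**The case against.** The best defence is that the lists are not closed. The extraction covers patient demographics, and the verb in "Demographic information will include age, race, and ethnicity" is not strictly exhaustive. The list in Data Analyses is demonstrably incomplete: the number of clinic visits is a stated control in Aim 2 Methods but is missing from the model sentence. On this view, sex is unnamed rather than excluded. That stands as far as it goes. However, sex, unlike clinic visits, is named in neither place, and the plan gives an analyst no instruction to use it.

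A second defence is that age, race and ethnicity literally satisfy an aim about demographic characteristics. This also stands in part: adding sex is a judgement about what such an aim should cover. It is also true that the mentions of gender identity in Aim 1 (diversity of the qualitative sample, an item in the online survey) do not show that the authors meant sex to be an Aim 2 predictor.

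Three stronger readings are tempting, and the documents do not support them:

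- A reader might infer that a sex disparity cannot be estimated. That is true of the specified analysis but not necessarily of the data, since sex may be among the extracted demographics.
- A reader might infer that the PTSD and pain coefficients are confounded by sex as well. The documents give nothing to support this, and a difference in sex mix by HIV status would not by itself bear on those coefficients.
- A reader might infer a material bias in the HIV contrast. The documents give no sex distribution and no sex effect, and under the main assumptions the shift is less than 6% in either direction.

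**Conclusion.** The point holds as a gap between the stated aim and the specified analysis. This part rests on the text alone and is certain. The effect on the HIV odds ratio is secondary: small under the main assumptions, modest under the least favourable ones, and of either sign depending on the direction of the sex effect. The gap is worth closing because Aim 2 exists to describe disparities and closing it costs almost nothing. It does not undermine the design or the model.

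**What to change.** Add sex to the demographic variables in Aim 2 Methods and to the fixed effects of the mixed model in Data Analyses, Aim 2. Confirm that it is among the patient demographics in the data request. Report its odds ratio with the other demographic contrasts. If there is a reason to leave sex out, state it.

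The same edit is a good occasion to give one complete covariate list, including the number of clinic visits, so that the two sections agree.

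The cost is one added model term and, if sex is not already in the extract, one added data field. If there are few women, the interval for the sex contrast will be wide, but that is a matter for reporting and not a reason to omit it.

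### Aim 2 enters pain only as annual mean ≥ 7 or not, so differences in dispensation below 7 cannot be seen; one supportive spline model per outcome would show them

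*Combined protocol and SAP*

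**What the plan says.** In the combined protocol and SAP, Aim 2 Methods describes the source variable: "Pain is coded 0-10 at each VHA healthcare visit as the fifth vital sign". The extraction list there includes "primary care/ID clinic outpatient healthcare encounters, pain intensity vital sign data, patient demographics", so the visit-level scores will be in hand. For analysis the scores "will be averaged over each 12-month monitoring period and dichotomized as severe (≥ 7) vs. mild/moderate (0-6"), with a published source cited for the cut.

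Data Analyses, Aim 2 specifies the model: "Generalized linear mixed modeling (GLMM) with a logit link and binomial variance will be used", with random effects for clinic and patient. The predictors listed end with "psychiatric disorder, and severe average pain in likelihood of pharmacotherapy dispensation during a given year". On entry the plan says "Covariates will be assessed for collinearity before entering them simultaneously into the GLMM". On outcomes, Aim 2 Methods says "For each year in which patients are determined to be smoking, three outcomes will be assessed": dispensation of NRT, of bupropion, and of any cessation drug.

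No section plans a continuous, banded or spline form of pain for Aim 2. The PEG pain scale in Table 1 is an Aim 3 measure and does not fill the gap.

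**The concern.** The annual mean has to be computed before it can be cut, and is then discarded. The model can answer one question about pain: whether dispensation differs between years with a mean of at least 7 and all other years. It cannot show whether dispensation rises, falls or stays flat between 0 and 7, where most patient-years probably lie. If the relation is graded, or changes at a lower level of pain, the reference group mixes patient-years with different dispensation rates. The estimated contrast is then diluted and less precise. Pain is one of the variables the plan examines for disparities, so a real pattern below 7 would go unreported.

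**Working it through.** **No figure to reproduce.** The documents give no Aim 2 sample size, power target, dispensation rate, pain distribution or share with severe pain. That differences below 7 cannot be seen follows from the text alone: one indicator at 7 fits one common level (on the logit scale, other covariates fixed) to every mean below 7.

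**Assumptions for the illustration (not from the documents).** Annual mean pain has mean 3 or 4 and SD 2 or 2.6, with a normal or a beta shape on 0-10. That gives eight scenarios. Patient-years are treated as independent, and other covariates and the random effects are ignored.

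**Where patient-years fall.** Across the eight scenarios P(≥ 7) runs from 0.023 to 0.162, so the reference group holds 1 − 0.162 = 84% to 1 − 0.023 = 98%. Of all patient-years, 22-43% have means from 4 to below 7.

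**Information kept by the split** is the R² of the true shape regressed on the indicator.

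- Linear truth, normal pain: φ(c)² / [p(1 − p)]. For mean 3, SD 2: c = (7 − 3)/2 = 2, φ(c) = 0.0540, p = 0.0228, so 0.0540² / (0.0228 × 0.9772) = 0.13. The highest value, 0.50, is the beta case with mean 4 and SD 2.6.
- Step at 4: p7(1 − p4) / [p4(1 − p7)], where p4 and p7 are the shares at or above 4 and 7. For normal, mean 3, SD 2: p4 = P(Z ≥ 0.5) = 0.3085, so 0.0228 × 0.6915 / (0.3085 × 0.9772) = 0.05. For beta, mean 3, SD 2.6: p7 = 0.103 and p4 = 0.103 + 0.215 = 0.318, so 0.103 × 0.682 / (0.318 × 0.897) = 0.25.

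**Comparison of codings.** The spline has knots at the 5th, 35th, 65th and 95th percentiles. Its joint test has 3 df, which needs a noncentrality of 10.90 for 80% power at 5%, against 7.85 for 1 df. The ratio is 7.85/10.90 = 0.72, and the last row multiplies by it.

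| Coding | Linear truth | Step at 4 | Step at 7 |
|---|---|---|---|
| ≥ 7 split | 13-50% | 5-25% | 100% |
| Linear term | 100% | 58-74% | 13-50% |
| Spline, before df penalty | 100% | 74-89% | 49-81% |
| Spline, after df penalty | 72% | 53-64% | 35-58% |

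After the penalty the spline is not the most powerful choice under any of the three shapes. Its lowest value, 35%, is better than the lowest for the linear term (13%) or the split (5%).

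**Effect of sample size.** In one simulated case (OR 1.15 per SD of pain, about 20% dispensation, four visits a year, about 14% severe), power was 74% with a linear term and 44% with the split at 2,000 patient-years, and 97% against 75% at 5,000. The loss can matter at moderate size and fades as the sample grows.

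**The printed lower band.** Scores of 6 and 7 average 6.5, which the label 0-6 does not name. In the eight scenarios 4-10% of means lie between 6 and 7.

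**The case against.** The cut at 7 is pre-specified, carries a citation and gives a contrast that is easy to state. The Purpose section frames Aim 2 around HIV status and demographic characteristics. Pain is not in that statement and appears only among the model's predictors. The data source is VA-wide records from 2014 onward, so the sample may be large enough that lost precision has no practical effect. Every percentage above depends on an assumed distribution, and the normal versions put 2-12% of patient-years below zero on a 0-10 scale. A linear term beats the spline for a linear effect and for a step at 4, so a reasonable statistician could choose a linear term or three bands. A second pain result for each outcome also invites the question of which one counts.

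Most of this stands. It is why the split should remain the planned result and why the spline should be labelled supportive. It does not remove the central point: a larger sample makes the single contrast more precise but never shows what happens below 7.

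A reader might infer that means between 6 and 7 are left unclassified. The text does not support that. A dichotomy with an explicit upper rule of ≥ 7 places everything else below it. Rounding the mean first would move some patient-years, but nothing in the plan suggests it. Writing < 7 is a wording clarification only.

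**Conclusion.** The point holds as a minor, inexpensive improvement to one secondary predictor. That differences below 7 cannot be seen is certain from the text. The loss of precision is conditional: the split keeps about 13-50% of the information under a linear association and 5-25% under a step at 4, given annual means averaging 3-4 with SD 2-2.6, independent patient-years and no random effects. If the effect is a step at 7, the planned split loses nothing and is the best coding. The case for a spline is that it shows the shape and has the best worst case among these shapes; greater power is not the reason.

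Two stronger readings are not supported. A reader might infer that coarse pain coding biases the HIV or demographic contrasts. The documents give nothing on how pain relates to those variables or to dispensation, so no such bias can be claimed. A reader might also infer that Aim 2 is underpowered for pain. With no sample size, effect size or dispensation rate stated, that cannot be judged.

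**What to change.** 1. In Aim 2 Methods, write the split as annual mean ≥ 7 versus < 7, and keep it as the planned contrast.
2. In Data Analyses, Aim 2, pre-specify for each of the three outcomes one supplementary GLMM with the same patient-years, other covariates and random effects. Replace the indicator with annual mean pain as a restricted cubic spline with 4 knots at the 5th, 35th, 65th and 95th percentiles. Report the joint 3-df test and the predicted probability of dispensation across 0-10.
3. State that these models are supportive and that the ≥ 7 contrast remains the planned result if the two differ.

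The cost is a small text edit and three extra models on a variable already derived, with no new data. The pain result becomes less simple to state. The 3-df test has less power than a linear term if the effect is linear, and less than the split if it is a step at 7.
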